Early Mobilization of Older Adults in the Cardiovascular Intensive Care Unit

I. RESEARCH QUESTION

Is an early progressive mobilization program safe, feasible, and effective in older adults in the Cardiovascular Intensive Care Unit (CICU)?

II. HYPOTHESES

1. An early mobilization (EM) program is safe, feasible, and effective in older adults in a Canadian tertiary care academic CICU.
2. Level of function on CICU discharge and time spent lying in bed during hospitalization is associated with health-related quality of life scores and functional status at longer-term follow-up.

III. SPECIFIC AIMS

Aim #1: To determine functional status and longer-term patient-centered outcomes of older adults admitted to the CICU prior to the implementation of the EM program (“pre-intervention” cohort)

Aim #2: To assess the safety and feasibility of an EM program in a Canadian academic tertiary care CICU

Aim #3: To determine the effectiveness of EM at improving the functional status of older adults during CICU admission and improving longer term patient-centered outcomes (“intervention” cohort)

Aim #4: To evaluate the association of daily time spent lying in bed with functional status at CICU discharge and following hospital discharge

Aim #5: To assess the amount of skeletal muscle mass loss during admission for acute cardiovascular disease

IV. BACKGROUND

A. Physical Function and Impairment in Older Adults in the Critical Care Unit

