To introduce the EM protocol to the nursing staff, the nurse and physician champion will provide a series of in-service training sessions. Physicians routinely caring for older adults in the CICU and rotating trainees will receive education in the CICU through “Lunch and Learn” conferences. Weekly audits will be performed by the nurse champion to assess for adherence to the EM protocol. Reminders and further education will be provided if necessary. Monthly status reports will be created and disseminated to the nurses and the CICU team.

Frailty will be assessed on admission using the Clinical Frailty Scale (CFS) by the patient’s nurse or a member of the research team (Appendix B).³² The CFS is a simple bedside assessment tool that uses a single global judgement-based measure to assign a score from 1 (very fit) to 9 (terminally ill) with increasing scores from 5 to 8 indicating more advanced frailty.²⁰ The CFS correlates with more comprehensive frailty tools, has been shown to accurately diagnose frailty in critically ill and acute cardiac populations, and provides short and long-term prognostic information.^{20, 21, 33}

Enrolled participants will be approached to participate in this prospective substudy. Patients accepting participation will be asked to wear an accelerometer monitor during CICU stay until the end of hospitalization to capture the time spent in each mobility position. Body composition parameters including skeletal muscle mass and fat mass will be measured daily with a segmental multi-frequency bioimpedance scale.

Instruments

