The ActiGraph GT9X Link Bluetooth Activity Monitor (ActiGraph, Pensacola, Florida) is an activity monitoring device worn on the thigh that uses a 3-axis accelerometer and inclinometer to provide information on position (lying, sitting, and standing), and physical activity (time spent walking and exercise intensity). The ActiGraph GT9X Link has been shown to accurately and reliably identify lying, sitting, standing and activity in hospitalized inpatients recovering from acute or critical illness.³⁴ It is superior in position identification compared to other commonly used accelerometers that use a dual-axis approach.³⁵ The device uses Bluetooth to communicate with the ActiLife software, which uses validated algorithms to differentiate between the various mobility positions.³⁵ Tabular and graphic displays of position data are automatically reported by the software. The average battery life of the device is 14 days, ensuring that it will not require recharging in the vast majority of participants. The monitors are to be removed temporarily if participants will be exposed to water (i.e., shower). The device is reusable and will be cleaned using standard isopropyl alcohol-based solutions as clinically required for disinfection and by the research coordinator between participants. The device includes a wear time sensor that detects if the device has been removed in order to measure compliance. Five Actigraph monitors will be purchased, so that up to five patients can be enrolled in the accelerometer substudy at a given time. The cost for five Actigraph monitors, software, and necessary support is \$4,280. An application for Investigational Testing Authorization will be submitted to Health Canada for the use of the Actigraph monitoring system. The Actigraph monitor has already been approved for investigational use in another Canadian-based research study.³⁶

The InBody 770 segmental multi-frequency bioimpedance (BIA) scale has been validated for the determination of skeletal muscle mass (Appendix A). The BIA scales are currently

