In the patients wearing the accelerometer, data will be recorded on the total time spent in each mobility position, the daily average time spent in each mobility position, the average duration of time for each bout of sitting, standing, and walking, and sleep duration. The step count will also be recorded. The change in skeletal muscle mass from CICU admission to hospital discharge will be recorded.

We will determine which covariates predict improvement in LOF (“responsiveness”) and which ones do not (“non-responsiveness”). We will assess the recovery of physical function at 1 month and 12 months as measured by the SF-36 physical component summary score. We will compare the SF-36 scores of the highest scoring tertile of LOF on hospital discharge with the lowest scoring tertile. We will also compare hospital readmission at 30 days and discharge home vs. healthcare facility.

For safety, we will record the composite and individual components of the number of falls, injuries, and dislodgements over the total number of attempted mobility activities. The results from the intervention cohort will be compared to the pre-intervention cohort for all results.

Data Collection Procedures

Following discharge, a member of the research team will capture the following hospitalization data from the electronic medical record (Chartmaxx, Quest Diagnostics, Madison, New Jersey) for each subject: age, sex, primary admission diagnosis, comorbidities, level of function assessments, CFS score, length of CICU stay, length of hospital stay, discharge location, and referral to cardiac rehabilitation.

Availability of Participants

In the fiscal year 2016-2017, there were 1,356 admissions to the JGH CICU (mean age 68 years old; 477 female (35%)). There were 1,034 patients (76.3%) age ≥ 60 years old. The mean CICU length of stay was 3.3 days and the mean hospital length of stay was 9.5 days. Only one in five patient stays was less than 24 hours in length.

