Appendix A: **Validation Studies of Segmental Multi-Frequency Bioimpedance (BIA)**

Study	N	Population	Fat Free Mass Mean ± SD	Correlation vs. DXA R	Bland-Altman vs. DXA Mean Difference (95% CI)
Alves 2014	55	Stable heart failure patients	57 ± 9 ♂ 39 ± 6 ♀	0.93	+0.1 (-4.9, +5.1)
Kim 2013	129	Community-dwelling women aged 75+	30.6 ± 3.5 ♀	0.92	-2.1 (-2.8, -1.8)
Furstenberg 2010	53	Hemodialysis patients	45.7 ± 10.1	-	+0.5 (-0.7, +1.7)
Bosy-Westphal 2013	254	Healthy volunteers aged 18-65	65.4 ± 6.6 ♂ 55.4 ± 11.8 ♀	0.99	+0.05 (-3.7, +3.7)
Leahy 2012	403	Healthy volunteers aged 18-29	66.7 ± 6.4 ♂ 46.2 ± 4.0 ♀	-	+0.6 (-4.9, +6.0) ♂ +2.0 (-2.1, +6.2) ♀
Ling 2011	484	Middle-aged adults from Leiden Longevity Study	63.6 ± 7.0 ♂ 46.5 ± 5.2 ♀	0.98	-1.5 (-4.0, +1.1) ♂ -0.8 (-3.2, +1.6) ♀
Shafer 2009	132	Healthy volunteers aged 19-72	68.1 ♂ 45.9 ♀	-	+0.3

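### Aim 5 reads a bioimpedance change as skeletal muscle loss, but the cited validation tabulates fat-free mass in non-acute populations, so fluid and muscle change cannot be told apart

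*Combined protocol and SAP*

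**What the plan says.** Aim 5 (section III) is "To assess the amount of skeletal muscle mass loss during admission for acute cardiovascular disease". Section VI gives the measurement just before Instruments: "Body composition parameters including skeletal muscle mass and fat mass will be measured daily with a segmental multi-frequency bioimpedance scale". Outcome Measures defines what is kept: "The change in skeletal muscle mass from CICU admission to hospital discharge will be recorded".

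The support for reading this as muscle is one sentence under Instruments, which states that the scale "has been validated for the determination of skeletal muscle mass (Appendix A"). The body-composition column of Appendix A is headed "Fat Free Mass Mean ± SD", and its agreement column "Bland-Altman vs. DXA Mean Difference (95% CI". The populations are "Stable heart failure patients", community-dwelling women aged 75 and over, "Hemodialysis patients", three healthy-volunteer samples and one middle-aged cohort.

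The only patients barred from the BIA substudy are those with a pacemaker or defibrillator. The Data Analysis section gives no analysis of muscle mass change.

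**The concern.** Aim 5 asks for an absolute quantity of tissue lost during an acute illness. For that, the measurement must follow change in muscle within a patient over days and must not respond materially to other things that change over the same days. The cited evidence covers neither requirement. It tabulates a compartment that contains water, in people not described as acutely ill, and compares methods between people rather than over time.

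If hydration differs between the first and last reading, the BIA change can move without any change in muscle. Net fluid loss would tend to look like muscle loss, and net fluid gain would tend to hide it. This is a possible shift in the mean, so a larger substudy would not remove it. The risk is that the trial publishes an amount of muscle loss that its measurement cannot support.

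**Working it through.** The plan states no sample size, effect size or SD of change for Aim 5, so there is no figure to reproduce. The check is mainly of the text; the arithmetic only gives scale.

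**1. Claim against evidence**

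| Needed for Aim 5 | What Appendix A offers |
|---|---|
| Skeletal muscle mass | Fat-free mass is the only compartment tabulated; the correlation and difference columns name none |
| Acute cardiovascular inpatients | Stable heart failure, older community women, hemodialysis, healthy volunteers, middle-aged adults |
| Change within a patient over days | Correlation and mean difference against DXA; no row reports agreement of change |

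The appendix title names the BIA technique, not the specific model.

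**2. Anything elsewhere that separates fluid from muscle?** None was found. The plan does not mention body weight, fluid balance, edema or diuresis. The extraction lists (Pre-intervention; Data Collection Procedures) hold no such variable. The example covariates in Data Analysis belong to the level-of-function (LOF) model and include no fluid term. Primary admission diagnosis is extracted.

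**3. Illustration of scale.** Assumptions, none from the documents: true muscle loss is zero, net fluid loss is F kg, and a share s of it is carried into the muscle estimate. Apparent muscle loss = F × s.

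| F (kg) | s = 0.25 | s = 0.50 | s = 1.00 |
|---|---|---|---|
| 1 | 0.25 | 0.50 | 1.00 |
| 5 | 1.25 | 2.50 | 5.00 |

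Counted wholly as fat-free mass, and using the stable heart failure means of 57 (men) and 39 (women), with kg assumed because the table gives no unit:
- F = 1: 1/57 = 1.8% in men and 1/39 = 2.6% in women.
- F = 5: 5/57 = 8.8% in men and 5/39 = 12.8% in women.

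**4. Appendix A's own spread.** The stable heart failure row gives +0.1 (−4.9, +5.1) with N = 55. The half-width is (5.1 + 4.9)/2 = 5.0.
- Read as limits of agreement, the SD of the BIA–DXA difference is 5.0/1.96 = 2.55.
- Read as a confidence interval for the mean, it is 5.0 × √55/1.96 = 18.9. That is implausible beside a fat-free mass SD of 9 in men and a correlation of 0.93, so limits of agreement is the likelier reading despite the column heading.

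The hemodialysis row gives +0.5 (−0.7, +1.7) with N = 53 and half-width 1.2. The SD is 1.2/1.96 = 0.61 as limits of agreement, or 1.2 × √53/1.96 = 4.5 as a confidence interval. The column may mix the two kinds of interval, so this row cannot safely be read as tight individual agreement.

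**The case against.** **Fluid change is not shown to pass into the muscle reading.** The device is segmental and multi-frequency, and the documents do not say how its muscle estimate treats water. This stands. A reader might infer that fluid shifts would be reported as muscle loss, or that every decongested patient will show a fall. The documents support only that the two could not be distinguished.

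**The illustration is not evidence.** Also right. Both inputs are assumed. A reader might go on to infer that the artefact is as large as a plausible true loss, but the documents give no expected true loss to compare it with.

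**Within-patient change cancels device error.** Constant bias does cancel, so the SD of 2.55 between methods is not the error of Aim 5's outcome. With correlation ρ between the errors of the two readings, the SD of the change error is 2.55 × √(2(1 − ρ)): 3.61 at ρ = 0 and 1.14 at ρ = 0.9. The documents do not give ρ. Error that follows hydration does not cancel if hydration differs between the readings.

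**Hemodialysis is a population with altered fluid status.** It is the nearest one listed, and it counts for something. It is still not described as acute, has no correlation, and reports a mean difference rather than agreement of change.

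**The cohort comparison would cancel the problem.** It would be less affected if fluid change were similar in both cohorts. Aim 5, however, asks for the absolute amount, and a different diagnosis mix could make fluid change differ between cohorts.

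**It is only a substudy measure.** True, and it limits the weight of the point. The primary LOF conclusions are untouched. A reader might extend the problem to an analysis of muscle loss by time lying in bed, but none is planned: Aim 4 relates lying time to functional status.

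**Conclusion.** The point holds for Aim 5 alone. The validity statement goes beyond its own citation, and the planned outcome cannot separate muscle change from fluid change. The direction of error would depend on whether a patient loses or gains fluid. Its size cannot be computed from the documents, and the 0.25 to 5 kg range only restates the assumptions of 1 to 5 kg fluid loss and 25% to 100% pass-through.

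The conclusion rests on three things: fat-free mass includes body water, hydration may differ between admission and discharge in this population, and no fluid measure is planned. It does not rest on any claim about how strongly this device responds to water. Correction is worthwhile because it changes what Aim 5 may conclude at almost no cost.

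**What to change.** 1. Under Instruments, state that the cited validation is for fat-free mass against DXA in the listed non-acute populations.
2. In Aim 5 and Outcome Measures, name the outcome *BIA-estimated change* and say that it combines fluid and lean-tissue change.
3. Report it separately for patients whose primary admission diagnosis is heart failure and for the rest, using the diagnosis already extracted. Draw no muscle-loss conclusion from the heart failure group. In the rest, any such conclusion still assumes little net fluid change, and the report should say so.
4. Optionally, add charted net fluid balance to the extraction list and show a fluid-balance-adjusted result beside the unadjusted one as a sensitivity analysis.

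Do not adjust for concurrent change in body weight or restrict to weight-stable patients. Body weight contains the muscle being measured: 1 kg of true muscle loss lowers weight by 1 kg. Adjustment would remove part of the target quantity. Restriction would drop patients who lost muscle and weight together, and keep those whose loss was offset by fluid or fat.

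Items 1 to 3 cost wording and one stratification. The muscle-loss claim becomes narrower and less precise. Item 4 adds one variable that is not on the current extraction lists.

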Level of Function 1	Bed Activity
Level of Function 2	Able to Sit
Level of Function 3	Able to Stand
Level of Function 4	Walks < 20 feet
Level of Function 5	Walks > 50 feet

The current mobility practices and LOF assessment for patients admitted to the CICU of the Jewish General Hospital were reviewed by a nurse educator on two separate dates as part of continuous quality improvement requested by the quality of care committee of the division of cardiology. We looked at a convenience sample of patients in the CICU on two separate dates. There were 26 patients in the analysis (mean age 71.7 years old, standard deviation (SD) ± 10.9 , female 38.4% (n=10)). There were 10 patients (38.5%) who would not be initially eligible for entry into the study (see eligibility criteria below; four due to age, two on noninvasive or invasive ventilation, two with a transvenous pacemakers, and two who were not hemodynamically stable). For patients who were initially eligible for the study, the mean prehospital LOF was 4.7 (SD ± 0.6) and the mean LOF on CICU admission was 2.3 (SD ± 1.2). Of the eligible patients, 14 patients (87.5%) said they would agree to participate in an EM study and 12 patients (75%) were followed prior to hospitalization by a hospital-affiliated cardiologist.

VI. METHODS

Design, participants and setting

An EM program is being developed as a quality improvement project in conjunction with the Quality and Safety Committee of the Division of Cardiology at the Jewish General Hospital (JGH). For our study, we will perform a prospective, pre/post-EM intervention study in adults aged ≥ 60 years old admitted to the CICU at the JGH. During a 3-month period, we will prospectively enrol patients to the pre-intervention cohort. The EM intervention will then be implemented. During a 12-month period, we will prospectively enrol patients to the intervention cohort. 1 and 12 months following hospital discharge, patients in the pre-intervention and post-intervention cohorts will be contacted by phone by a member of the research team to assess for functional status and quality of life measures.

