housed in the Frailty Assessment Unit of the JGH's cardiovascular ward and can be used at the point of care. The BIA scales provide a full analysis of body composition in less than 1 minute, including determination of skeletal muscle mass. There are no risks associated with the bioimpedance scale, except for patients with a permanent pacemaker or defibrillator, who will be excluded from this trial (the reason being that bioimpedance scale currents may disrupt the functioning of pacemakers or defibrillators).

Post-discharge follow-up

One month and 12-months post-discharge a member of the research team will call participants by phone to assess for health-related quality of life and functional status. The member of the research team will determine the current LOF and administer the Short-Form 36-Item Health Survey (SF-36) and Barthel index.

Outcome Measures

The primary outcome will be the LOF at CICU discharge and at 1 and 12 months post-hospitalization. Secondary outcomes are (1) Short Form (SF)-36 physical component summary score at 1 and 12 months, (2) SF-36 mental component summary score at 1 and 12 months, (3) Barthel index score at 1 and 12 months, (4) length of hospital stay, and (5) discharge to healthcare facility (including rehabilitation facility, convalescence, transfer to another acute care facility, and long-term care placement).

The SF-36 is a patient-reported survey of health and is the most widely used health-related quality of life instrument.⁵³ The physical and mental component scores are subsets of the SF-36 with score ranges from 0-100 and are calibrated for an average score of 50, using Canadian normative data, with higher scores indicating less disability.⁵⁴ The Barthel index is a disability measure validated in elderly cardiac patients that incorporates ten activities of daily living (i.e., feeding, dressing, incontinence).^{55, 56} Only two components of the Barthel index address mobility issues (transfer and mobility), so there is minimal direct overlap with the LOF scale score. The score range is 0–20, with lower scores indicating increased disability.

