A research assistant will be based in the Division of Cardiology at the JGH and will have a dedicated space and workstation with computer access in the clinical research department. The research assistant will be responsible for obtaining informed consent, extracting data from the patient record, putting it into the database system, auditing nursing adherence to the study protocol, publishing monthly status updates, and interviewing patients by phone. Funds to support a research assistant on a part-time basis (20 hours per week) will be provided for a one-year period by the JGH's Division of Cardiology.

The EM team has support and representation from leaders in various disciplines at the JGH including [name], the head of the CICU nursing department, [name], Chief of the JGH Division of Cardiology and Director of the Integrated Cardiovascular Science Program, [name], Chief of Cardiac Surgery, and [name], Director of the CICU.

The JGH’s Division of Cardiology has given me approximately 50% protected research time with a salary support of \$50k per annum to pursue my research program. I also receive a salary support for research of \$20k per annum from the JGH’s Department of Medicine. Funds to support a research assistant on a part-time basis (20 hours per week) for a 1 year period – renewable for up to 3 years - will be provided by the cardiology division as well.

VIII. KNOWLEDGE DISSEMINATION

We will develop simple to follow instructional materials, including the detailed EM protocol and videos on how to perform the level of function assessment and mobility activities. These will be made available on a dedicated web portal.

We intend to publish the EM protocol and the study results in a peer-reviewed cardiology journal, as well as present the findings at a major national cardiology conference. Through membership in the Canadian Cardiovascular Critical Care Society, a member society of the Canadian Cardiovascular Society, the results of the study will be disseminated to healthcare professionals involved in acute cardiovascular care.

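### LOF at 1 and 12 months, two of the three primary time points, is left to an unmasked telephone caller, so caller judgement can create or inflate a longer-term EM effect

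*Combined protocol and SAP*

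**What the plan says.** Section VI, Outcome Measures: "The primary outcome will be the LOF at CICU discharge and at 1 and 12 months post-hospitalization".

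Section VI, Post-discharge follow-up: at 1 and 12 months a research team member "will call participants by phone to assess for health-related quality of life and functional status". On the call, "The member of the research team will determine the current LOF and administer the Short-Form 36-Item Health Survey (SF-36) and Barthel index". The secondary outcomes thus have named instruments. For the phone LOF, this section gives no questions and no scoring rule.

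Section VII names the role that makes the calls. "The research assistant will be responsible for obtaining informed consent, extracting data from the patient record", and the same sentence goes on to list "auditing nursing adherence to the study protocol, publishing monthly status updates, and interviewing patients by phone". Under Data Collection Procedures in Section VI, the extracted record includes the level-of-function assessments. Extraction takes place after discharge, and nothing requires it to wait for a call.

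On adherence audits the plan says two things. Section VII lists them among the research assistant's duties, while Section VI, Intervention, says "Weekly audits will be performed by the nurse champion to assess for adherence to the EM protocol".

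On design: "we will perform a prospective, pre/post-EM intervention study in adults aged ≥ 60 years old admitted to the CICU at the JGH". Enrolment runs for 3 months before the program starts and for 12 months after. "The results from the intervention cohort will be compared to the pre-intervention cohort for all results".

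Neither blinding nor an independent assessor is mentioned anywhere in the document.

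**The concern.** The long-term part of Aim 3 rests on comparing LOF after discharge between two cohorts that were not randomised. If the person who assigns the level knows the cohort and may already have seen the patient's in-hospital LOF, a generous reading of borderline answers in the EM cohort looks the same in the data as a real benefit. The planned cumulative logit model with generalised estimating equations handles correlation between repeated measurements. It cannot remove a scoring error that differs by cohort.

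The scale makes this matter more. LOF has few levels, and recovered patients are likely to sit near the top, so one borderline decision between levels 4 and 5 moves a patient across the cut that carries most of the information. SF-36 and Barthel are collected on the same calls, but as standard questionnaires they leave the caller less discretion.

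**Working it through.** **Step 1. What the caller can know.** The text on the caller, set side by side:

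- Consent: the research assistant (Section VII) obtains it during the CICU admission (Section VI), so this role meets the patient in a known period.
- Record: the same role extracts it, including in-hospital LOF.
- Call date: Section XI puts enrolment in months 0-3 and 4-16. Ignoring hospital stay (mean 9.5 days), 1-month calls fall at about months 1-4 against 5-17, and 12-month calls at about months 12-15 against 16-28. At either follow-up point the two windows hardly overlap, so the date largely identifies the cohort.

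The audit duty is not needed for this step.

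**Step 2. No figure to reproduce.** The plan states no effect size, alpha or error rate for LOF. What follows is an illustration on assumed values.

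**Step 3. Assumed share at LOF 5.** The only local LOF data are the pilot figures in Section V: 26 − 10 = 16 initially eligible patients, prehospital mean 4.7, SD 0.6. Twelve patients at level 5, three at 4 and one at 3 fit: mean = (60 + 12 + 3)/16 = 4.69, SD = 0.60. That puts 12/16 = 75% at LOF 5. It is an assumption that LOF after discharge resembles prehospital LOF, so 60% is shown as well.

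**Step 4. Odds ratio produced by scoring alone.** Let p be the true share at LOF 5 in both cohorts and d the share of EM patients wrongly scored as 5:

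OR = [(p + d)/(1 − p − d)] / [p/(1 − p)]; share of below-5 EM patients upgraded = d/(1 − p).

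| p | d | Upgraded among those below 5 | LOF-5 odds ratio |
|---|---|---|---|
| 0.75 | 0.05 | 0.05/0.25 = 20% | 4.00/3.00 = 1.33 |
| 0.75 | 0.10 | 0.10/0.25 = 40% | 5.67/3.00 = 1.89 |
| 0.60 | 0.05 | 0.05/0.40 = 12.5% | 1.857/1.50 = 1.24 |
| 0.60 | 0.10 | 0.10/0.40 = 25% | 2.333/1.50 = 1.56 |

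**Step 5. Against the expected numbers.** Section VI, Availability of Participants, expects 75 and 300 patients. With z = ln(OR)/SE and SE² = 1/(75p) + 1/(75(1 − p)) + 1/(300(p + d)) + 1/(300(1 − p − d)):

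- p = 0.75, d = 0.10: 0.636/0.312 = 2.04
- p = 0.75, d = 0.05: 0.288/0.303 = 0.95
- p = 0.60, d = 0.10: 0.442/0.267 = 1.65
- p = 0.60, d = 0.05: 0.214/0.265 = 0.81

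At an assumed two-sided 5% level (critical value 1.96), only the most extreme case would be expected to reach significance. Smaller errors still raise the false-positive rate. In a simulation with LOF capped at 5 (mean 4.7, SD about 0.6, Mann-Whitney test, one time point), moving 20% or 30% of below-5 EM patients up one level gave about 11% or 19% false positives, against about 5% with no mis-scoring.

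**Step 6. Dilution over three time points.** Discharge LOF is not scored by the caller. Suppose one cohort effect is fitted across all three time points, with the 12/3/1 distribution at each (a strong simplification) and only level-4 patients upgraded. The share at LOF 5 in the EM cohort then averages (75 + 80 + 80)/3 = 78.3% or (75 + 85 + 85)/3 = 81.7%. The LOF-5 odds ratio is (78.3/21.7)/3 = 1.20 or (81.7/18.3)/3 = 1.48. A proportional-odds fit to the same distributions gives 1.19 and 1.44; for a single time point it gives 1.30 and 1.79.

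**The case against.** **The LOF tool may already have anchors.** Section VI, Pre-intervention, refers to Appendix A for LOF, but the Appendix A in the supplied text holds bioimpedance validation studies. Section VI describes the tool as quantitative, and the related scale in Section V uses observable levels. A reader might infer that the level is free judgement with no rule behind it. The documents do not support that, because the tool cannot be inspected and the verb *determine* may mean no more than asking the patient. What stands is that the follow-up section does not say how a bedside scale becomes a level over the telephone, and leaves that step to an unmasked caller.

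**The caller may not audit adherence.** A reader might infer from Section VII that the scorer also polices the program under test. Section VI gives the weekly audits to the nurse champion, so the inference is not secure. The two sections must be reconciled, but the point does not depend on the answer.

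**One person in every role is an inference.** Section VI says only that a member of the research team calls, and whether one individual consents a patient and makes the 12-month call is not stated. This is fair. A different caller would still be unmasked and would still know the date.

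**The illustration may run high.** No passage supports an error of 5 or 10 percentage points. The larger case at 75% requires upgrading two in five EM patients below level 5, and the odds ratios concern one cut at one time point. This is accepted, and the figures are labelled accordingly.

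**SF-36 and Barthel offer a check.** They do, in part: a phone LOF benefit without any movement on either would be suspect. They come from the same unmasked calls, so agreement among the three would not settle the matter.

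**Conclusion.** The point holds as a possibility that the design leaves open. Two of three primary time points are assigned by telephone by a research team member. The role named for the calls also takes consent and has access to in-hospital LOF, and no masking is described. In a sequential before/after comparison this can create or inflate a 1- or 12-month EM effect.

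The size is unknown. On assumed values, for one cut at one time point, scoring alone gives an LOF-5 odds ratio of 1.33 to 1.89 with 75% truly at level 5, or 1.24 to 1.56 with 60%. It is closer to 1.2 to 1.5 when averaged over three time points on the simplification in Step 6. These figures show how sensitive the outcome is. A reader might take them as a forecast of bias, or as proof that a real effect could never be told apart from scoring. The documents support neither reading. The change is a worthwhile and inexpensive improvement.

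**What to change.** In Section VI, Post-discharge follow-up, replace the instruction to determine the current LOF with a fixed script of closed mobility questions that the patient answers, and have the database assign LOF from the answers by a stated rule. Use the identical script in both cohorts from the first pre-intervention call; introducing it later would make measurement itself differ by cohort. Show the caller no earlier LOF during the call. Where two team members are available, the caller should not be the one who consented the patient or abstracted the chart. State that SF-36 and Barthel from the same calls will be read alongside LOF as a partial cross-check. Reconcile Sections VI and VII on who audits adherence.

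The cost is a one-page script and a database rule, with no extra staff. The caller may still infer the cohort from the date or from having met the patient, and patients know what care they received, so some bias remains. Hiding the cohort on a contact sheet would add little for the same reason. Holding all chart abstraction until after the 12-month call would not clearly be free, so neither is part of this request.
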